### 14.3 Healthcare utilization

In the only recent study that compared non-protocol-driven healthcare utilization using the incidence rates of healthcare days as an outcome measure among patients with OUD receiving opiate substitution therapy with either Sublocade® or placebo, the data demonstrated a combined emergency room visit or hospital day incidence rate of 2.01 healthcare days per 1 000 patient days in the Sublocade® group versus 6.97 healthcare days per 1 000 patient days in the placebo group. These rates likely underrepresent the current rates of healthcare utilization in Canada as the study was conducted in 2015 and the patients included in the trial were residents of the United States and 60% had no medical insurance likely creating barriers to healthcare access and lowered rates of utilization that would not exist for Canadian patients who have universal and free access to acute healthcare services. There have been no direct comparisons between Sublocade® and Suboxone® treatments. As a result, a sensitivity analysis

using different inputs has been conducted given that the maximum person days exposure for each patient is 365 days. We also assume a worse-case scenario of loss-to-follow-up (for any reason) of 50% over the study period, a rate of loss-to-follow-up much higher than the 20% rate reported by Ling *et al.*

**Table 4: Sensitivity analysis for attainable power to detect a range of differences in the incidence rates of healthcare days between treatment groups with different sample sizes**

Variable 	Scenarios	
	1	2
Comparator group incidence	2.0	2.4
Group difference in incidence rates	1.0	1.2
Sample size per group (patient days) 	3650	3650
Power	99	99

 Incidence = total number (hospital days + emergency room visits)/1 000 patient days; Assumptions: 2-sided  $\alpha$  level of 0.05; 50% loss-to-follow-up

 Sample size per group derived from a sample of 20 patients \* 365 days exposure/patient \* 0.5 (=50% rate of loss-to-follow-up)

#### 14.4 Final sample size

In a hierarchical 3-level mixed effects model with 45 and 45 level 2 units (RAAM clinic patients) randomized to Suboxone® and Sublocade® in a 1:1 ratio, 4 level 3 units (RAAM clinics) in total and an average of 5 level 1 units (RFWs) per level 2 unit, 90.0% power is achieved to detect a difference in RFWs proportions of at least 0.15, where the Suboxone® and Sublocade® RFWs proportions are 0.3 and 0.45, respectively, assuming that the correlation between level 1 units in a level 2 unit is 0.8 and the correlation between level 2 units in a level 3 unit is 0.025, and the 2-sided test is performed at the 5% significance level. Using even a much smaller sample size (N=20 patients per group with 50% loss-to-follow-up over 12-month study period), a 2-sided comparison of two incidence rates (number of healthcare days per 1000 patient days exposure) with a sample size of 3650 patient days exposure per group would achieve 99% power at the 0.05 significance level to detect a difference in incidence rates of at least 1 if the Suboxone® group incidence rate was 2.

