Date of first enrollment	November 1, 2022
Target sample size	90
Recruitment status	Not yet started
Primary outcome(s)	
1) Difference in proportion of relapse-free weeks (time-frame; 12 months)
 
2) Difference in incidence rates of opioid-related healthcare utilization (time-frame; 12 months)

Key secondary outcome(s)	
1) Difference in Medication Satisfaction Questionnaire scores
 
2) Difference in World Health Organization Quality of Life – BREF Questionnaire scores
 
3) Difference in proportion of patients who attend <math>\geq 80\%</math> of scheduled clinic visits
 
4) Difference in opioid-related mortality proportions

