
### 14.2 Opioid positivity

Previous studies have used a simple data generating model for opioid positivity in which the difference in proportions of opioid positivity, regardless of how opioid positivity was defined, never accounted for the clustering of repeated measures of opioid positivity by individual and site. This dramatically reduces the power to detect differences in proportions of opioid positivity between treatment groups. For example, for our trial to detect a difference in proportion of RFWs of  $\geq 0.15$  with a power of 80% using a Z-test (unpooled variance) significance level at the 2-sided  $\alpha$  level of 0.05 would require 160 patients per group if the comparator group's RFWs proportion is 0.3 (estimated from Lofwall *et al.*). Contrast this to a

data generating model that more appropriately accounts for clustering of opioid positivity observations. In this study, a mixed model using a 3-level hierarchical design will be used to describe the relationship between repeated measures of opioid positivity (Level 1) obtained from individual patients (Level 2) recruited from 4 different RAAM clinic sites (Level 3), where Level 2 patients will be randomized to either Sublocade® or Suboxone®. In addition to the assumption of a comparator group RFWs proportion of 0.3, if we also assume a Level 1 unit correlation of 0.8, a Level 2 correlation of 0.025, and an average of 5 repeated measures of opioid positivity per Level 2 patient over the study period, then we would need only 34 patients per treatment group to detect a difference in RFWs proportion of  $\geq 0.15$  with a power of 80% and a mixed model test significance level at the 2-sided  $\alpha$  level of 0.05. Sensitivity analysis using different values for the variables used in the hierarchical model assumptions (Table 3) demonstrates that the upper range of sample sizes is consistently less than 70 per group.

**Table 3: Sensitivity analysis for sample size estimations needed to detect  $\geq 15\%$  difference between RFWs proportions between treatment groups for a mixed model test in a 3-level hierarchical design (Level 2 randomization)**

Variable 	Scenario 									
	1	2	3	4	5	6	7	8	9	10
Power	80	80	80	80	80	80	80	80	90	90
Comparator group RFW proportion	0.3	0.3	0.3	0.3	0.1	0.6	0.3	0.3	0.3	0.3
Level 1 unit correlation	0.8	0.5	0.99	0.99	0.99	0.99	0.8	0.8	0.99	0.99

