Level 2 unit correlation	0.025	0.025	0.1	0.001	0.001	0.001	0.025	0.025	0.001	0.001
Level 3 units	4	4	4	4	4	4	3	2	4	3
Average number of Level 1 units per Level 2 units	5	5	5	5	5	5	5	5	5	5
Sample size per group	34	24	37	41	42	38	45	68	41	54

 Assumptions: 2-sided  $\alpha$  level of 0.05; Difference in RFWs proportion  $\geq 0.15$ ; Treatment group allocation = 1:1

 Highlighted cells (Yellow) represent changes from preceding scenario

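### Section 14.4 claims 90.0% power for relapse-free weeks with 45 patients per arm; its own inputs give about 37%

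*Combined protocol and SAP*

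**What the plan says.** Section 14.4 describes a three-level mixed model "with 45 and 45 level 2 units (RAAM clinic patients) randomized to" the two treatments, with 4 clinics in total and an average of 5 measures per patient. It assumes a correlation of 0.8 between measures in a patient and 0.025 between patients in a clinic, proportions of relapse-free weeks of 0.30 and 0.45, and a two-sided 5% test. It concludes that "90.0% power is achieved to detect a difference in RFWs proportions of at least 0.15". The "Target sample size" in section 1.1 is 90, so 45 is the whole arm.

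Section 14.2 gives the reasoning. It says that earlier trials "never accounted for the clustering of repeated measures of opioid positivity by individual and site" and lost power as a result. A simple Z-test at 80% power "would require 160 patients per group if the comparator" proportion is 0.30. Once clustering is modelled, with 5 measures per patient and correlations of 0.8 and 0.025, it says "then we would need only 34 patients per treatment group to detect a difference in RFWs proportion of" 0.15 or more. Table 3 varies the inputs, and the text concludes that "the upper range of sample sizes is consistently less than 70 per group".

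**The concern.** Repeated measures that agree at 0.8 within a patient are largely copies of one another. Allowing for that correlation can save a little over one observation per patient, but it cannot reduce the number of patients by a factor of almost five. Table 3 also behaves oddly. Patients are randomized within clinics, yet the printed "Sample size per group" doubles when the number of clinics halves.

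Relapse-free weeks is the first primary endpoint, and the target of 90 rests on this power figure. Section 14.1 sets 0.15 as the clinically important difference and says the result is meant for providers, policy makers and insurers. If power is far below 90%, a null result could easily be taken as evidence of no benefit when the trial was unlikely to detect the benefit it was designed for.

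**Working it through.** **Inputs, all from section 14.4.** n = 45 patients per arm; m = 5 measures per patient; ρ1 = 0.8 within patient; ρ2 = 0.025 within clinic; proportions 0.30 and 0.45, so d = 0.15 and the mean is 0.375; two-sided 5%.

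**Step 1. Reproduce the 160 in section 14.2.** With one observation per patient and unpooled variance: (1.96 + 0.842)² × (0.30×0.70 + 0.45×0.55) / 0.15² = 7.849 × 0.4575 / 0.0225 = 159.6, so 160. This figure is correct.

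**Step 2. Value of five measures.** With ρ1 = 0.8, five measures are worth 5/(1 + 4×0.8) = 1.19 independent ones. Randomizing within clinics removes the clinic component, so the variance factor becomes 1 + (m−1)ρ1 − mρ2 = 1 + 3.2 − 0.125 = 4.075, and the value is 5/4.075 = 1.23. The saving takes 160 to about 130 (unpooled) or 133 (pooled), not to 34.

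**Step 3. Power at 45 per arm.** SE = √[2 × 0.375 × 0.625 × 4.075 / (5×45)] = √(0.46875 × 4.075 / 225) = 0.0921. Then d/SE = 1.628 and power = Φ(1.628 − 1.960) = 37.0% (37.7% unpooled).

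**Step 4. Simulation.** Correlated binary measures in 4 clinics, with a clinic-adjusted comparison of patient proportions, gave 36.6% at 45 per arm (8,000 trials; false-positive rate 4.9%), 81.8% at 136 per arm and 90.8% at 180 per arm (4,000 trials each).

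**Step 5. Patients needed per arm for 0.15.** N = (1.96 + z)² × 0.46875 × 4.075 / (5 × 0.0225).
- 80% power: 7.849 × 16.98 = 133.3
- 90% power: 10.507 × 16.98 = 178.4

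With 45 per arm, 80% power requires a true difference of 0.264.

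**Step 6. Table 3's other inputs, 45 per arm and 5 measures.**

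| Proportions | ρ1 / ρ2 | Power |
|---|---|---|
| 0.30 vs 0.45 | 0.5 / 0.025 | 49% |
| 0.30 vs 0.45 | 0.8 / 0.025 | 37% |
| 0.30 vs 0.45 | 0.99 / 0.1 | 34% |
| 0.30 vs 0.45 | 0.99 / 0.001 | 31% |
| 0.10 vs 0.25 | 0.99 / 0.001 | 47% |
| 0.60 vs 0.75 | 0.99 / 0.001 | 33% |

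Even 70 per arm, more than any count in Table 3, gives 53% on scenario 1's inputs.

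**Step 7. Probable cause (an inference).** Scenarios 1, 7 and 8 differ only in the number of clinics: 4×34 = 136, 3×45 = 135, 2×68 = 136. Dividing the formula's total per arm by the number of clinics gives:

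| Row | Formula per clinic per arm | Printed |
|---|---|---|
| Scenario 1 | 33.3 | 34 |
| Scenario 2 | 23.5 | 24 |
| Scenario 3 | 36.5 | 37 |
| Scenario 4 | 40.5 | 41 |
| Scenario 5 | 25.0 | 42 |
| Scenario 6 | 37.9 | 38 |
| Scenario 7 | 44.4 | 45 |
| Scenario 8 | 66.6 | 68 |
| Scenario 9 | 54.2 at 90% power; 40.5 at 80% | 41 |
| Scenario 10 | 72.3 at 90% power; 54.0 at 80% | 54 |
| Section 14.4 design | 44.6 at 90% power | 45 |

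Scenarios 1–4, 6 and 7 and the final 45 fit after rounding up, and scenario 8 is off by one. Scenario 5 does not fit. Scenarios 9 and 10 are labelled 90% but match 80%; scenarios 4 and 9 print the same 41 although they differ only in power. The document does not show whether inputs or counts are wrong in scenarios 5, 9 and 10.

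**The case against.** The strongest objection is that this is not the planned analysis. Section 20.11a specifies a three-level mixed logistic model with a random slope on severity and a week-by-treatment interaction, whereas the formula and the simulation compare proportions. That limits what the 37% means: it is the power of the calculation in section 14.4, conditional on its inputs, and not a forecast for the trial.

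Secondly, the plan will collect more than 5 measures: section 12.11 schedules a test every 2 weeks over 48 weeks, which is 24. At a correlation of 0.8 this barely helps, giving 38.2% with 24 measures and 38.4% with 48. It matters more if the correlation is lower. With 24 measures, power is 55% at a correlation of 0.5, and 90% is reached at about 0.20; with 5 measures the correlation would have to be about 0.04. Section 14.2 cites no source for 0.8, so true power could lie outside the 31% to 49% range. None of this supports the stated 90.0%, which is tied to 0.8 and 5 measures.

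Thirdly, the per-clinic explanation is inferred without the software output, and three of ten scenarios do not fit it. That is fair, but the result in steps 1 to 5 does not use it. Reading 45 as a per-clinic count would restore the power (180 per arm gives 90.3%), but the registered target of 90 rules it out.

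**Conclusion.** The power statement is wrong as written. On section 14.4's own inputs, 45 patients per arm give about 37% power for a 0.15 difference, so a true gain of that size would be missed about 63% of the time. Across Table 3's settings with a 0.30 comparator and 5 measures, the chance of missing it is about 51% to 69%. The claimed fall from 160 to 34 per group is not possible with five measures correlated at 0.8.

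These figures assume the plan's proportions and correlations, equal allocation within clinics, and a comparison of proportions. The finding concerns only the first primary endpoint; healthcare utilization has its own power statement. Confidence is high on the arithmetic, lower on the cause. This must be fixed before the plan is relied on.

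**What to change.** 1. Re-run the calculation, confirm whether the software's output is per clinic or per arm, and give totals per arm in section 14.2, Table 3 and section 14.4.
2. In section 14.2, delete the claim that modelling clustering reduces the requirement from 160 to 34, and correct the statement that every scenario stays under 70 per group.
3. In section 14.4, replace 90.0% with the power from the re-run. The check here gives about 37% for 0.15 (31% to 49% over Table 3's settings with a 0.30 comparator and 5 measures), or about 80% for a difference of about 0.26. State whether 90 patients is kept on that basis.
4. Re-run and reconcile scenarios 5, 9 and 10 without presuming whether the inputs or the counts are at fault.

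The cost is protocol wording and a less favourable stated power; no extra enrolment is required. If the sponsor prefers to keep 90% power for 0.15, 178.4 per arm rounds up to 179, or 358 in total. At section 15's 1 to 2 patients per week, that is 179 to 358 weeks of recruitment against 45 to 90 weeks for 90 patients.

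### The 99% power claimed for healthcare utilization at 3650 patient-days per group is wrong: the plan's own rates give about 7 versus 4 expected healthcare days and 12% to 20% power

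*Combined protocol and SAP*

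**What the plan says.** Healthcare utilization is one of two primary outcomes (sections 1.1, 7.1 and 12.12). Its power is addressed only in section 14.3 with Table 4, and in the last sentence of section 14.4.

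Table 4 fixes the unit in its first footnote: "Incidence = total number (hospital days + emergency room visits)/1 000 patient days". It lists two scenarios, a comparator rate of 2.0 with a difference of 1.0 and a comparator rate of 2.4 with a difference of 1.2. Each has 3650 patient-days per group and a power of 99. The second footnote explains the exposure: "Sample size per group derived from a sample of 20 patients", multiplied by 365 days and by 0.5 for loss to follow-up.

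Section 14.4 repeats the claim in prose: a two-sided test "with a sample size of 3650 patient days exposure per group would achieve 99% power at the 0.05 significance level to detect a difference". It sets that difference at 1 or more and assumes that the Suboxone "group incidence rate was 2", both per 1000 patient-days. It presents this as what a far smaller trial than the planned 45 per group would achieve.

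**The concern.** The rates are per 1000 patient-days, but the exposure is counted in single patient-days. With 3650 patient-days and rates of 2 and 1 per 1000, each group contributes only a handful of events, and no ordinary two-sided test separates counts that small with near certainty.

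This matters because the outcome carries the economic case. Section 14.1 chooses a 50% reduction as the target because a saving of that size would recoup the drug cost, and section 5.2 says the trial is needed to demonstrate cost-effectiveness and justify wider access. As written, a reader or ethics board would conclude that this endpoint is powered with ample margin at 20 patients per group. If it is in fact underpowered at 45 per group, a non-significant result would be inconclusive about a 50% reduction, yet could be read as evidence that there is no cost offset.

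**Working it through.** **Inputs** (sections 14.3 and 14.4, Table 4)
- Rates: 2 versus 1 per 1000 patient-days (scenario 1); 2.4 versus 1.2 (scenario 2).
- Exposure per group: 20 × 365 × 0.5 = 3650 patient-days.
- Two-sided alpha 0.05, 1:1 allocation. The planned analysis is Poisson regression with exposure (section 20.11b).

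**Formula.** With equal exposure and expected counts m1 and m2, normal-approximation power is Φ((m1 − m2)/√(m1 + m2) − 1.96).

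**Trying to reproduce 99% (scenario 1)**
- Expected counts: 3650 × 0.002 = 7.3 and 3650 × 0.001 = 3.65.
- z-ratio: 3.65/√10.95 = 1.10. Power = Φ(1.10 − 1.96) ≈ 19.6%.
- On the log rate ratio, the scale of Poisson regression: ln 2/√(1/7.3 + 1/3.65) = 1.08, so power is 19.0%.
- Other tests: square-root transform 20.0%, score 17.7%, mid-p 17.5%, exact conditional 11.9%.

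**Scenario 2.** Counts 8.76 and 4.38; z-ratio 4.38/√13.14 = 1.21; normal power 22.6%. The range across tests is 15% to 23%.

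**Other readings tried (scenario 1 unless stated)**
- One-sided normal tests: about 29% to 30%.
- No loss to follow-up (7300 days per group): 27% to 36%.
- Rates read per 100 days: 93% to 94% (scenario 2: 96% to 97%).
- Rates read per single day: counts 7300 and 3650, z-ratio 3650/√10950 ≈ 35, power essentially 100%.

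Of these two-sided readings, only the last reaches 99%.

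**A check against the plan's own source figures.** Section 14.3 cites 2.01 on Sublocade versus 6.97 on placebo per 1000 patient-days. Even that contrast, at 3650 days per group (counts 7.34 and 25.44), gives about 89% by the normal formula.

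**Power of the planned design.** 45 × 365 = 16,425 patient-days per group with full follow-up; half of that is 8,212.5.

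| Scenario and exposure per group | Expected counts | Normal | Log ratio | Exact | Range over all tests |
|---|---|---|---|---|---|
| 1, 3650 days | 7.3 / 3.65 | 19.6% | 19.0% | 11.9% | 12–20% |
| 1, 8,212.5 days (45 per group, 50% loss) | 16.4 / 8.2 | 38.0% | 36.8% | 30.4% | 30–39% |
| 1, 16,425 days (45 per group, full) | 32.9 / 16.4 | 64.8% | 63.1% | 60.7% | 61–66% |
| 2, 16,425 days (45 per group, full) | 39.4 / 19.7 | 72.7% | 71.0% | 69.5% | 70–74% |

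**Exposure needed (scenario 1).** Days per group = (1.96 + z)² × (0.002 + 0.001)/0.001².
- 80% power: (1.96 + 0.842)² × 3000 ≈ 23,550 days, about 65 patients per group with full follow-up or 129 with 50% loss.
- 99% power: (1.96 + 2.326)² × 3000 ≈ 55,100 days, about 151 or 302 patients per group. This is 15 times the stated 3650.

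**Overdispersion.** One admission can produce several healthcare days, so days cluster within patients. The documents give no variance ratio. If ratios of 2, 3 and 5 are assumed, the full-follow-up z-ratio of 2.34 in scenario 1 is divided by √2, √3 and √5. Power falls from 65% to about 38%, 27% and 18%.

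**The case against.** The arithmetic has no good defence: the per-1000 unit appears in both the table footnote and the prose, and nothing elsewhere corrects it. The serious objections concern reach.

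- **Cause.** The nQuery inputs are not shown, so a dropped unit is an inference. Rates per single day would give 100% rather than 99%, unless the output was capped or rounded. This stands, but the error does not depend on how it arose.
- **True rates may be higher.** Section 14.3 says the cited rates probably understate Canadian use, and the 2.01 it cites is a Sublocade rate, not a Suboxone rate. If comparator rates of 3 or 4 per 1000 are assumed, with the same halving, 45 per group with full follow-up gives about 82% or 91% (normal). So the shortfall at 45 per group is conditional on the plan's tabulated rates. It does not rescue the claim: at 4 versus 2, 3650 days give Φ(7.3/√21.9 − 1.96), about 34%.
- **Loss may be well under 50%.** Section 18.22 continues follow-up of routinely collected outcomes after withdrawal, and section 18.13 obtains utilization by record linkage. This is fair, and the full-follow-up figures already grant it.
- **The figure did not set the sample size.** The 45 per group comes from the opioid-positivity model. That limits the consequence, but this is still the only power statement for a primary outcome.

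**Conclusion.** The concern holds. The stated 99% cannot be obtained from the plan's own inputs; the correct figure is 12% to 20% for 2 versus 1 per 1000 patient-days, and 15% to 23% for 2.4 versus 1.2. At 45 per group with complete follow-up, neither tabulated scenario reaches 80%: 61% to 66% in the first and 70% to 74% in the second. With the plan's worst-case 50% loss, the first scenario gives 30% to 39%.

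These figures rest on independent Poisson events, equal exposure and the plan's rates. Clustering of days within patients would lower them; a higher true comparator rate would raise them. A unit slip is the likely explanation but cannot be confirmed from the documents. A primary outcome is presented as comfortably powered when the design does not deliver that power at the assumed rates, so the text must be corrected.

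**What to change.** - In Table 4, replace 99 with 12% to 20% (scenario 1) and 15% to 23% (scenario 2), or give one figure and name the test. The log rate ratio is closest to the planned Poisson regression and gives 19% in scenario 1.
- In section 14.4, delete the claim that a much smaller sample is enough. State the power at 45 per group instead: for scenario 1, 61% to 66% with full follow-up and 30% to 39% with 50% loss; for scenario 2, 70% to 74% with full follow-up. Say that linkage may keep loss below 50%.
- Add a sensitivity range for overdispersion, labelled as an assumption, and for higher comparator rates if the sponsor believes Canadian use exceeds 2.4 per 1000 patient-days.
- State that, at the assumed rates, a non-significant result on this outcome will not rule out a 50% reduction, and that the rate ratio will be reported with its confidence interval.

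The cost is a revision to sections 14.3 and 14.4 and a less favourable figure. The correction changes no procedure and does not itself require more patients. Whether to enlarge the trial or to present this outcome as limited in power is then an informed choice for the sponsor.

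### The 99% power stated for healthcare utilization does not follow from its inputs (they give about 12% to 20%), and the base rates behind it are unsupported

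*Combined protocol and SAP*

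**What the plan says.** Section 14.3 takes its rates from one placebo-controlled study, which gave "2.01 healthcare days per 1 000 patient days in the Sublocade® group" and 6.97 on placebo. It comments that "These rates likely underrepresent the current rates of healthcare utilization in Canada", and that "There have been no direct comparisons between Sublocade® and Suboxone® treatments". No Suboxone rate appears anywhere in the documents. Because of that gap, the section offers Table 4 as a sensitivity analysis. Its two scenarios are "Comparator group incidence 2.0 2.4" and "Group difference in incidence rates 1.0 1.2", each with 3650 patient-days per group and each with a stated power of 99.

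Section 14.4 repeats the result in words. For "a 2-sided comparison of two incidence rates" the claim reads "sample size of 3650 patient days exposure per group would achieve 99% power at the 0.05 significance level". That power is said to apply when the aim is "to detect a difference in incidence rates of at least 1 if the Suboxone ® group incidence rate was 2". The section presents this as holding even with only 20 patients per arm and half of the follow-up lost. Section 14.1 sets the target effect at a 50% reduction, on cost grounds. Section 20.11b plans a Poisson regression.

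**The concern.** Utilization is one of two primary outcomes and carries the plan's cost-effectiveness argument. A reader of 14.4 would conclude that this endpoint is amply powered at less than half of the planned enrolment. Two things cast doubt on that.

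- **The figure.** Rates of 2 and 1 per 1000 days over 3650 days produce only a handful of events, far too few for 99% power.
- **The rates.** A Suboxone rate of 2.0 or 2.4 with a difference of 1.0 or 1.2 puts Sublocade at 1.0 or 1.2. The only Sublocade rate cited is 2.01, and the plan expects Canadian rates to be higher. It gives no reason for planning lower.

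If both stand, a null result on utilization could be read as evidence of no effect when the trial had a modest chance of seeing the effect it calls important.

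**Working it through.** **Inputs.** Rates of 2.0 vs 1.0 and 2.4 vs 1.2 per 1000 patient-days (Table 4, 14.4). Exposure per arm is 20 × 365 × 0.5 = 3650 days (Table 4 footnote). Two-sided alpha is 0.05. The planned enrolment is 45 per arm (14.4).

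**Formula.** With expected counts m = rate/1000 × patient-days and Poisson variance, z = (m1 − m2)/√(m1 + m2), and power = Φ(z − 1.96).

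**The plan's own figure (stated: 99%).**

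- Scenario 1: m1 = 7.30, m2 = 3.65. z = 3.65/√10.95 = 1.103. Power = Φ(−0.857) ≈ 20%.
- Scenario 2: m1 = 8.76, m2 = 4.38. z = 4.38/√13.14 = 1.208. Power = Φ(−0.752) ≈ 23%.

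Other methods for scenario 1 give 19% (log rate ratio), 20% (square-root transform), 12% (exact conditional binomial) and 29% (one-sided Wald). None approaches 99%. Reading 2 and 1 as rates per single patient-day gives essentially 100%, so a units slip is possible, but the documents do not show it. For 99% power at 2 vs 1 per 1000 days, the exposure needed is (1.960 + 2.326)² × 0.003/0.001² ≈ 55,100 days per arm, or about 151 patients per arm followed for 365 days. Even the full placebo contrast in the source (6.97 vs 2.01) would give only 88.5% at 3650 days.

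**Base rates against the cited source.** The planned Sublocade rates are 1.0/2.01 = 50% and 1.2/2.01 = 60% of the cited rate. Both scenarios have a rate ratio of 0.5 and the same exposure, and their base rates differ by a factor of 2.4/2.0 = 1.2. Table 4 therefore does not explore the uncertainty that it was set up to address.

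**Power at 45 per arm (Wald, no overdispersion).** Exposure is 45 × 365 × 0.5 = 8212.5 days with 50% loss, and 45 × 365 = 16,425 days with full linkage. The rates 4.02 vs 2.01 apply the plan's 50% effect to the cited Sublocade rate. The rates 3.01 vs 2.01 keep the absolute difference of 1. Both Suboxone rates are assumptions.

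| Suboxone vs Sublocade, per 1000 days | 3650 days | 8212.5 days | 16,425 days |
|---|---|---|---|
| 2.0 vs 1.0 | 20% | 38% | 65% |
| 4.02 vs 2.01 | 35% | 65% | 91% |
| 3.01 vs 2.01 | 13% | 25% | 44% |

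The exact test gives 12%, 30% and 61% for the first row, and 27%, 61% and 90% for the second.

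**Overdispersion.** Hospital days come in runs: section 5.12 gives a median stay of 3 days and a range of 1 to 207. The 3.65 days expected on Sublocade in scenario 1 are thus about one median admission. Dividing z by the square root of an assumed variance inflation, at 45 per arm with full linkage:

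- Inflation 3: 2.340/√3 = 1.351, power 27% for 2.0 vs 1.0; 3.317/√3 = 1.915, power 48% for 4.02 vs 2.01.
- Inflation 10: 11% and 18%.

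**The case against.** The plan is open about the evidence gap. It says that no head-to-head data exist, words the Suboxone rate of 2 as a condition, and labels Table 4 a sensitivity analysis. Enrolment of 90 rests on the relapse-free-weeks calculation, so utilization is only a supporting check. Utilization comes from database linkage (18.13) and follow-up for it continues after withdrawal (18.22), so near-full exposure at 45 per arm is a realistic case. A Sublocade rate below 2.01 is also possible: this trial counts only opioid-related days under listed codes (12.12), whereas 14.3 describes the source measure as non-protocol-driven utilization and states no such restriction. Finally, at a fixed 50% reduction a low base rate lowers power, so the choice is conservative.

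Most of this stands. It means that 2.01 belongs in a range and should not be imposed as the Sublocade input, and that enrolment need not change. It does not rescue the 99%, which is wrong at the plan's own inputs, and it does not supply the missing reason for a Sublocade rate of 1.0. The conservative direction also applies only to a fixed ratio. With the absolute difference held at 1, moving Sublocade up to 2.01 lowers power (44% against 65% at full linkage).

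**Conclusion.** The stated 99% is incorrect: at 3650 patient-days per arm the inputs give about 20% (Wald) or 12% (exact). The base rates are unexplained and sit uneasily with the one source cited. At 45 per arm with Poisson variance, power runs from about 25% to 91% across the rates and exposures considered, and overdispersion would lower it. These figures rest on assumed Suboxone rates and assumed variance inflation, since the documents give neither.

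A reader might go further in two ways that the documents do not support.

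- **That the plan sized the wrong contrast by giving Suboxone the Sublocade rate.** The contrast sized is Suboxone against Sublocade at a 50% reduction, which is the plan's own target in 14.1. The closeness of 2.0 to 2.01 is striking, but nothing says that one was taken from the other.
- **That the low base rate produced the 99%.** It cannot have done so: going from 2.0 vs 1.0 to 4.02 vs 2.01 raises power from 20% to 35% at the same exposure.

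**What to change.** In Table 4 and section 14.4, delete the 99% figures and the implication that 20 patients per arm with 50% loss are enough. Restate power for 45 per arm, with rates and exposure in the same units, at both 50% loss and full linkage.

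Replace the two near-identical scenarios with a stated range of base rates. It can include 2.0 vs 1.0, 4.02 vs 2.01 and 3.01 vs 2.01, with Suboxone rates between 2.01 and 6.97 labelled as assumptions. In 14.3, give the reason for each arm's rate on the opioid-related endpoint. State there that no Suboxone rate is available and that the source rate is not described as opioid-related only. Add an overdispersion allowance, showing for example variance inflation of 3.

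The cost is a rewrite of 14.3, Table 4 and 14.4 and a few lines of power code, with no change to patients, procedures or enrolment. The downside is a less favourable power statement that depends openly on assumptions.
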